11.1.3 Severity of AEs

11.1.3.1 Identify the AE using the NCI Common Terminology Criteria for Adverse Events (CTCAE) version 4.0. The CTCAE provides descriptive terminology and a grading scale for each adverse event listed. A copy of the CTCAE can be found at

http://ctep.cancer.gov/protocolDevelopment/electronic_applications/ctc.htm

AEs will be assessed according to the CTCAE grade associated with the AE term. AEs that do not have a corresponding CTCAE term will be assessed according to the general guidelines for grading used in the CTCAE v4.0. as stated below.

CTCAE v4.0 general severity guidelines:

Grade	Severity	Description
1	Mild	Mild; asymptomatic or mild symptoms; clinical or diagnostic observations only; intervention not indicated.
2	Moderate	Moderate; minimal, local or noninvasive intervention indicated; limiting age-appropriate instrumental activities of daily living (ADL)*.
3	Severe	Severe or medically significant but not immediately life-threatening; hospitalization or prolongation of hospitalization indicated; disabling; limiting self-care ADL**.
4	Life-threatening	Life-threatening consequences; urgent intervention indicated.
5	Fatal	Death related to AE.

ADL

*Instrumental ADL refers to preparing meals, shopping for groceries or clothes, using the telephone, managing money, *etc.*

**Self-care ADL refers to bathing, dressing and undressing, feeding self, using the toilet, taking medications, and not bedridden.

11.1.4 Assessment of relationship of AE to treatment

The possibility that the adverse event is related to study agent will be classified as one of the following: not related, unlikely, possible, probable, definite.

11.1.5 Follow-up of AEs

All AEs, including lab abnormalities that in the opinion of the investigator are clinically significant, will be followed according to good medical practices and documented as such.

11.2 Serious Adverse Events

11.2.1 DEFINITION: Fed. Reg. 75, Sept. 29, 2010 defines SAEs as those events, occurring at any dose, which meet any of the following criteria:

- Results in death
- Is life threatening (*Note: the term life-threatening refers to an event in which the patient was at risk of death at the time of the event; it does not refer to an event which hypothetically might have caused death if it were more severe*).
- Requires inpatient hospitalization or prolongation of existing hospitalization
- Results in persistent or significant incapacity or substantial disruption of the ability to conduct normal life functions
- Is a congenital abnormality/birth defect
- Important medical events that may not result in death, be life-threatening or require hospitalization may be considered serious when, based upon appropriate medical judgment, they may jeopardize the patient or subject and may require medical or surgical intervention to prevent one of the outcomes listed.

11.2.2 Reporting SAEs to DCP

11.2.2.1 The Lead Organization and all Participating Organizations will report SAEs on the DCP SAE form found at http://prevention.cancer.gov/sites/default/files/uploads/clinical_trial/SAE-Form.pdf.

11.2.2.2 Contact the DCP Medical Monitor by phone within 24 hours of knowledge of the event.

DCP Medical Monitor:
[name]
Chief
Lung & Upper Aerodigestive Cancer Research Group
Division of Cancer Prevention, NCI, NIH
[name]
[name] (For FedEx, use [name])
[contact]
[contact]
email: [contact]

Include the following information when calling the Medical Monitor:

- Date and time of the SAE
- Date and time of the SAE report
- Name of reporter
- Call back phone number
- Affiliation/Institution conducting the study
- DCP protocol number
- Title of protocol
- Description of the SAE, including attribution to drug and expectedness

11.2.2.3 The Lead Organization and all Participating Organizations will email (preferred) or FAX written SAE reports to the DCP Medical Monitor within 48 hours of learning of the event using the paper SAE form. The written SAE reports will also be FAX'ed [contact]) or emailed ([contact]) to DCP's Regulatory Contractor, CCS Associates ([contact]).

11.2.2.4 The DCP Medical Monitor and regulatory staff will determine which SAEs require FDA submission.

11.2.2.5 The Lead Organization and all Participating Organizations will comply with applicable regulatory requirements related to reporting SAEs to the IRB/IEC.

11.2.3 Follow-up of SAE

Site staff should send follow-up reports as requested when additional information is available. Additional information should be entered on the DCP SAE form in the appropriate format. Follow-up information should be sent to DCP as soon as available. SAE related to the study agent will be followed until resolved, or deemed unlikely to further resolved by the Protocol Chair, or until the subject withdraws consent for further follow-up. SAE unrelated or unlikely to be related to study agent will be followed for at least 30 days after the last dose of study agent.

12. STUDY MONITORING

12.1 Data Management

This study will report clinical data using the OnCore application from Forte Research Systems, Inc., as stated in the Master Data Management Plan. All users of the database will have appropriate education, training and experience to perform assigned tasks. The data collection and management will be done according to the Consortia 2012 DMP.

12.2 Case Report Forms

Participant data will be collected using protocol-specific case report forms (CRF) developed from the standard set of DCP Chemoprevention CRF Templates and utilizing NCI-approved Common Data Elements (CDE). The approved CRFs will be used to create the electronic CRF (e-CRF) screens in the OnCore application. Consortia site staff will enter data into the e-CRF for transmission to DCP according to pre-established DCP standards and procedures. Amended CRF will be submitted to the DCP Protocol Information Office for review and approval. Approved changes will be programmed into the OnCore database by the Consortium Data Management staff.

CRF Submission Information:

University of Arizona Early Phase Chemoprevention Consortium Office
Attn: [name]
[name]
[name]
[contact]
[contact]
Email: [contact]

12.3 Source Documents

Source documentation for this trial will consist of protocol-specific source documents as well as clinical and research laboratory reports. In the event of a Serious Adverse Event, medical records related to the event will be sought for source documentation of the event and its treatment, if any.

12.4 Data and Safety Monitoring Plan

The University of Arizona Cancer Center (UACC) Data and Safety Monitoring Board (DSMB) will provide oversight for subject safety for all UA Consortium clinical trials consistent with the National Institutes of Health Policy for Data and Safety Monitoring dated June 10, 1998; further guidance statement issued by the NIH on June 5, 2000, and the policy for Data and Safety Monitoring by Data and Safety Monitoring Boards. The UACC DSMB meets quarterly.

Regular monthly meetings of the UA Consortium, are used as a forum to review accrual rates, problematic issues relating to accrual and protocol implementation, adverse events occurrence, follow-up, and reporting; submission of all required study reports; and progress and outcomes of laboratory analyses.

12.5 Sponsor or FDA Monitoring

The NCI, DCP (or their designee), pharmaceutical collaborator (or their designee), or FDA may monitor/audit various aspects of the study. These monitors will be given access to facilities, databases, supplies and records to review and verify data pertinent to the study.

12.6 Record Retention

Clinical records for all participants, including CRFs, all source documentation (containing evidence to study eligibility, history and physical findings, laboratory data, results of consultations, *etc.*), as well as IRB records and other regulatory documentation will be retained by the Investigator in a secure storage facility in compliance with Health Insurance Portability and Accountability Act (HIPAA), Office of Human Research Protections (OHRP), Food and Drug Administration (FDA) regulations and guidances, and NCI/DCP requirements, unless the standard at the site is more stringent. The records for all studies performed under an IND will be maintained, at a minimum, for two years after the approval of a New Drug Application (NDA). For NCI/DCP, records will be retained for at least three years after the completion of the research. NCI will be notified prior to the planned destruction of any materials. The records should be accessible for inspection and copying by authorized persons of the Food and Drug Administration. If the study is done outside of the United States, applicable regulatory requirements for the specific country participating in the study also apply.

12.7 Cooperative Research and Development Agreement (CRADA)/Clinical Trials Agreement (CTA)

Not applicable.

13. STATISTICAL CONSIDERATIONS

13.1 Study Design/Description

This study is a phase IIa single-arm, open-label trial in individuals with oral leukoplakia or erythroplakia to explore the potential of metformin for oral cancer prevention. The primary endpoint analysis is to determine whether 12-14 weeks of treatment with therapeutic doses of metformin would improve the clinical response of oral premalignant lesions. The clinical response of each participant will be evaluated. A response rate of

30% is considered as poor treatment and a response rate of 60% is considered as a good treatment. No early stopping rules due to futility or efficacy will be implemented.

13.2 Randomization/Stratification

This is a single-arm, open-label trial so no randomization, stratification or blocking will be performed. Also, no formal interim analysis is planned.

13.3 Accrual and Feasibility

The study plans to accrue 26 eligible participants to initiate agent intervention. With a projected attrition rate of 20%, we anticipate to have at least 20 participants completing the agent intervention to provide study endpoint data. The planned duration of accrual is 24 months with the expected accrual rate of 1 per month among three study sites.

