3. SUMMARY OF STUDY PLAN

The study is a phase IIa single-arm, open-label trial in individuals with oral leukoplakia or erythroplakia to explore the potential of metformin for oral cancer prevention. The study plans to accrue 26 eligible participants to initiate agent intervention. With a projected attrition rate of 20%, we anticipate to have at least 20 participants completing the agent intervention to provide study endpoint data. The plan duration of accrual is 24 months with the expected accrual rate of 1 per month among the three study sites.

Individuals with oral leukoplakia or erythroplakia will be recruited from local hospitals, Veterans Administration hospitals, pathology services, dental schools, dentist networks, and from advertising in local media.

Participants will undergo a Baseline Testing/Pre-Study Evaluation in which the informed consent form and medical records release and tissue release form will be signed. Participants will be assessed for study eligibility. Detailed inclusion and exclusion criteria are listed in sections 4.1 and 4.2. Participants will undergo a brief physical exam including chest, heart, abdomen, assessment of lower extremities for pedal edema, weight, height, vital signs (temperature, blood pressure, pulse) and performance status. They will also be evaluated for concomitant medications, medical history, baseline symptoms and signs, and assessment of tobacco and alcohol use. Participants will undergo an oral exam for lesion measurement, photography. Bi-dimensional measurements for all lesions will be recorded. All lesions that meet the size criteria ($\geq 8 \times 3$ mm) will be considered target lesions for clinical response assessment. Lesions that do not

meet the size criteria ($<8 \times 3 \text{mm}$) will be measured but recorded as non-measurable.

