8.3 Off-Agent Criteria

Participants may stop taking study agent for the following reasons: completed the protocol-prescribed intervention, adverse event or serious adverse event, inadequate agent supply, noncompliance, concomitant medications, medical contraindication. Participants will continue to be followed, if possible, for safety reasons and in order to collect endpoint data according to the schedule of events.

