13.4 Primary Objective, Endpoint(s), Analysis Plan

The primary objective of this study is to determine whether 12-14 weeks of treatment with therapeutic doses of metformin would improve the clinical response of oral premalignant lesions. Each participant's clinical response will be categorized into Complete Response (CR), Partial Response (PR), No Change (NC) or Progressive Disease (PD), evaluated by the criteria described in § 8.1. A participant with CR or PR is considered as a respondent. The preclinical data demonstrate that metformin defers carcinogen-induced HNSCC development and progression (see §2.3). Based on the positive preclinical data, the main interest of this study is in measuring and evaluating the improvement not in evaluating the unlikely negative effect. Therefore, a one-sided one-sample binomial exact test at a significance level of 5% will be performed to see if the clinical response rate is greater than 30% (poor treatment). A sample size of 20 achieves 87% power to detect a response rate 0.30 higher than a poor treatment response.

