13.5 Secondary Objectives, Endpoints, Analysis Plans

The secondary objectives of this study are to evaluate the histologic response to metformin intervention, to determine the metformin effect on cell proliferation and its molecular targets, to determine the metformin effect on frequent dysregulated molecular mechanisms and OCT expression, and to determine the impact of genomic alterations on the biological and biochemical consequences and clinical response to metformin.

Additional secondary objectives include evaluation of the metformin effect on serum metabolic markers, measurements of metformin concentrations in serum and saliva, and evaluation of metformin effect on serum and saliva inflammatory and angiogenic cytokines.

Similar to the primary endpoint, the histologic response rate will be calculated and a one-sided 95% confidence interval based on the exact method will be derived. Based on a small sample size of 20, nonparametric methods, e.g. signed rank test, will be performed to evaluate each of the changes in tissue, serum, and saliva markers. In addition, a univariate logistic regression model with the clinical response as the outcome variable will be fitted to explore if any of the expression of frequent dysregulated mechanisms, OCT3 levels, and any genomic alterations is associated with the clinical response to metformin.

To identify statistically significant changes in the saliva microbiome before and after metformin treatment, we will first evaluate changes in alpha diversity among matched pairs using non-parametric analogous Wilcoxon rank-sum test (Mann-Whitney test). To test for significant differences in beta diversity (e.g. if pre-treatment and post-treatment samples cluster in principle coordinates analysis space), permutational multivariate analysis of variance (PERMANOVA) will be used. Importantly, we are currently performing experiments in healthy volunteers to define the stability of the saliva microbiome over the course of a day

and in response to routine perturbations (e.g. brushing teeth, eating a meal). The results from these experiments will allow us to determine the appropriate effect size and assess potential correlations between the saliva microbiota and therapeutic outcome.

With an anticipated attrition rate of 20%, we will try to reduce the fraction of participants with missing outcomes as much as possible. Also, multiple imputation techniques will be used to handle missing data.

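### Does 24 months of accrual at 1 per month undermine the target of 26 starters and the 20 completers behind the 87% power?

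*Combined protocol and SAP*

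**What the plan says.** Section 13.3 (Accrual and Feasibility) gives the target first: "The study plans to accrue 26 eligible participants to initiate agent intervention". Allowing for 20% attrition, it continues: "we anticipate to have at least 20 participants completing the agent intervention to provide study endpoint data". It then forecasts the pace: "The planned duration of accrual is 24 months with the expected accrual rate of 1 per month among three study sites". Section 3 (Summary of Study Plan) has the same target, attrition and pace: "The plan duration of accrual is 24 months with the expected accrual rate of 1 per month among the three study sites". The two sections therefore agree with each other.

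Section 13.4 bases the primary analysis on a one-sided exact binomial test at 5% against a response rate of 30%, and states: "A sample size of 20 achieves 87% power to detect a response rate 0.30 higher than a poor treatment response". Section 12.4 says of the monthly consortium meetings that they "are used as a forum to review accrual rates", together with accrual problems. No section gives a calendar date or a month at which enrolment must stop.

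**The concern.** Within each of sections 3 and 13.3, rate times duration does not equal the target: 24 months at 1 per month is 24 starters, against 26 planned. The two missing participants fall at an awkward place. With 20% attrition, 20 completers need 25 starters. The target of 26 clears that by one and the forecast pace misses it by one. Keeping 20 completers tolerates 23.1% attrition from 26 starters but only 16.7% from 24, and the plan projects 20%.

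If the stated rate and duration were used as the yardstick at the monthly meetings, accrual could look on schedule while heading for two starters too few. Expected completers would then be about 19, where the exact test has about 81% power instead of 87%.

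**Working it through.** **Inputs.** Target 26 starters, attrition 20%, at least 20 completers, 24 months, 1 per month in total across the three sites (sections 3 and 13.3). Null response rate 0.30, alternative 0.60, one-sided exact binomial test at 5%, n = 20 (sections 13.1 and 13.4).

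**1. The plan's own chain.** Completers = starters × (1 − attrition).
- 26 × 0.8 = 20.8, so the figure of at least 20 reproduces as an expectation.
- Starters needed for 20 completers: 20 / 0.8 = 25. The target of 26 covers this with one to spare.
- Power at n = 20: the smallest cutoff keeping the error rate at or below 5% is 10 responders. P(X ≥ 10 | 0.30) = 0.0480 and P(X ≥ 10 | 0.60) = 0.8725. The stated 87% reproduces.

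**2. The accrual forecast.** Starters = rate × months.
- 1 × 24 = 24, short of 26 by 2 (2/26 = 7.7%).
- Rate needed for 26 in 24 months: 26/24 = 1.083 per month, which rounds to 1.
- Time needed for 26 at exactly 1 per month: 26 months, two more than planned.

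**3. If enrolment did stop at 24 starters.** This is hypothetical, since the documents contain no such stop.
- 24 × 0.8 = 19.2 expected completers.
- Attrition tolerated while keeping 20: 1 − 20/24 = 16.7%, against 1 − 20/26 = 23.1% from 26.
- Assuming independent 20% attrition, the chance of fewer than 20 completers is 54% from 24 starters and 25% from 26.

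**4. Exact power by number evaluable** (smallest cutoff with error rate ≤ 5%):

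| n | Cutoff | Error rate | Power at 0.60 |
|---|---|---|---|
| 18 | 10 | 0.0210 | 73.7% |
| 19 | 10 | 0.0326 | 81.4% |
| 20 | 10 | 0.0480 | 87.2% |
| 21 | 11 | 0.0264 | 82.6% |
| 22 | 11 | 0.0387 | 87.9% |
| 23 | 12 | 0.0214 | 83.6% |
| 24 | 12 | 0.0314 | 88.6% |
| 25 | 12 | 0.0442 | 92.2% |
| 26 | 13 | 0.0255 | 89.2% |

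Power rises and falls with n because the cutoff is a whole number. That is a property of every exact binomial design. From 19 to 26 evaluable, power stays between 81.4% and 92.2%.

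**The case for a change.** The strongest case for a change is that a section devoted to feasibility should multiply out to its own target, and that the gap falls across the plan's own requirement of 25 starters. The text does not say that the rate is rounded, so a reader cannot be sure that 1 means 1.08. The arithmetic in this case stands: 24 is not 26.

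The consequence does not stand. It needs enrolment to close at month 24 whatever the count, and no section says so. Section 12.4 names accrual rates as a topic for the monthly meetings but sets no yardstick, and a team counting starters against 26 would see that two were missing.

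A second argument is that n = 20 is a favourable point on the power curve. The most likely completer count from 26 starters is 21, with 82.6% power, and even full accrual leaves a 25% chance of fewer than 20 completers. Those figures are right if attrition is independent at 20% and only completers are analysed. The plan, however, aims to analyse more than completers. Section 8.3 says of those who stop the agent: "Participants will continue to be followed, if possible, for safety reasons and in order to collect endpoint data". Section 13.5 adds that "multiple imputation techniques will be used to handle missing data", and section 13.8 assesses everyone with endpoint data. If all 26 contributed, power would be 89.2%. Quoting power at the planned evaluable number is ordinary practice, and the figure quoted is correct. Giving a range for 19 to 22 instead would omit both 73.7% at 18 and the higher values at 24 to 26, so it would not be a clear improvement.

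**Conclusion.** No change to the plan is needed. The forecast pace falls two starters short of the target (24 against 26), a clerical mismatch explained by rounding 1.08 per month to 1. The target of 26, the expectation of at least 20 completers (20.8) and the 87% power at 20 evaluable (87.2%) are all correct. A team following the plan enrols 26 and runs the same test with the same power. The practical effect is about two more months of accrual if the rate is exactly 1 per month, and none if it is about 1.1.

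This rests on reading the 26 starters as the commitment and the duration and rate as expectations, which is how both sections word them, and on 1 per month being the combined rate for the three sites. It would be different if enrolment had a fixed closing date at month 24; the documents contain none.

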13.4 Primary Objective, Endpoint(s), Analysis Plan

The primary objective of this study is to determine whether 12-14 weeks of treatment with therapeutic doses of metformin would improve the clinical response of oral premalignant lesions. Each participant's clinical response will be categorized into Complete Response (CR), Partial Response (PR), No Change (NC) or Progressive Disease (PD), evaluated by the criteria described in § 8.1. A participant with CR or PR is considered as a respondent. The preclinical data demonstrate that metformin defers carcinogen-induced HNSCC development and progression (see §2.3). Based on the positive preclinical data, the main interest of this study is in measuring and evaluating the improvement not in evaluating the unlikely negative effect. Therefore, a one-sided one-sample binomial exact test at a significance level of 5% will be performed to see if the clinical response rate is greater than 30% (poor treatment). A sample size of 20 achieves 87% power to detect a response rate 0.30 higher than a poor treatment response.

13.5 Secondary Objectives, Endpoints, Analysis Plans

The secondary objectives of this study are to evaluate the histologic response to metformin intervention, to determine the metformin effect on cell proliferation and its molecular targets, to determine the metformin effect on frequent dysregulated molecular mechanisms and OCT expression, and to determine the impact of genomic alterations on the biological and biochemical consequences and clinical response to metformin.

Additional secondary objectives include evaluation of the metformin effect on serum metabolic markers, measurements of metformin concentrations in serum and saliva, and evaluation of metformin effect on serum and saliva inflammatory and angiogenic cytokines.

Similar to the primary endpoint, the histologic response rate will be calculated and a one-sided 95% confidence interval based on the exact method will be derived. Based on a small sample size of 20, nonparametric methods, e.g. signed rank test, will be performed to evaluate each of the changes in tissue, serum, and saliva markers. In addition, a univariate logistic regression model with the clinical response as the outcome variable will be fitted to explore if any of the expression of frequent dysregulated mechanisms, OCT3 levels, and any genomic alterations is associated with the clinical response to metformin.

To identify statistically significant changes in the saliva microbiome before and after metformin treatment, we will first evaluate changes in alpha diversity among matched pairs using non-parametric analogous Wilcoxon rank-sum test (Mann-Whitney test). To test for significant differences in beta diversity (e.g. if pre-treatment and post-treatment samples cluster in principle coordinates analysis space), permutational multivariate analysis of variance (PERMANOVA) will be used. Importantly, we are currently performing experiments in healthy volunteers to define the stability of the saliva microbiome over the course of a day

and in response to routine perturbations (e.g. brushing teeth, eating a meal). The results from these experiments will allow us to determine the appropriate effect size and assess potential correlations between the saliva microbiota and therapeutic outcome.

With an anticipated attrition rate of 20%, we will try to reduce the fraction of participants with missing outcomes as much as possible. Also, multiple imputation techniques will be used to handle missing data.

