7.6.3 Standard Biopsy Procedures

7.6.3.1 Local anesthetic: topical anesthesia consisting of viscous lidocaine, or topical application of 20% benzocaine, will be initially applied, and then the biopsy site will be injected with 1 or 2% lidocaine with or without 1:1000,000 epinephrine.

7.6.3.2 Incisional biopsy:

Lesion Biopsy

- For the baseline biopsy, using a Baker 4 mm punch, the center or clinically most suspicious area of the lesion is biopsied with a twisting motion. The circular punched out tissue is grasped gently with fine toothed forceps and excised just deep to the submucosa with the #15 scalpel. Care is taken to avoid collecting significant amounts of fat or muscle and to avoid crushing the specimen.
- Biopsy sample is placed mucosa side up on a clean hard surface such as a piece of wax paper, Whatman filter paper, or equivalent.
- The specimen will be oriented on the Whatman paper to further reduce artifact and preserve orientation. The specimen will be sent to the institutional pathology lab in 10% formalin (see section 10.2) for paraffin embedding, routine histopathology and stored for biomarker analyses.
- The above collection procedure will be utilized in an identical fashion for the post-treatment biopsy. The biopsy will be obtained from the most suspicious part of the lesion adjacent to the baseline biopsy. If no lesion persists post-treatment, then the biopsy will be taken from the site adjacent to the original biopsy.

Biopsy of visually normal cheek mucosa

A 3 mm punch biopsy will be collected from visually normal cheek mucosa in the similar fashion as the lesion biopsy.

7.6.3.3 Hemostasis is achieved by either direct pressure or suture, or silver nitrate stick.

7.6.3.4 Participants are provided with oral wound care instructions: 4-6 times daily local rinsing with saline and standard post surgical instructions including notification of consulting professional for heavy bleeding, severe pain, or fever.

7.6.3.5 For analgesia, participants will be told to take acetaminophen 325-650 mg po qid PRN. However, it is anticipated that the participants will not require significant pain control after the above procedure. Care should be taken to avoid Stenson's duct by greater than 1 cm after it is identified.

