8.2 Secondary Endpoints (in order of priority)

8.2.1 Histologic response to metformin intervention in the target lesion

Histologic response will be evaluated by the following criteria:

Complete Response (CR): Complete reversal of dysplasia or hyperplasia to normal epithelium in the target lesion.

Partial Response (PR): Improvement of the degree of dysplasia or hyperplasia in the target lesion.

No Change (NC): No change in the degree of dysplasia or hyperplasia in the target lesion, anything that is not CR, PR or PD.

Progressive Disease (PD): Increase in the severity of grade of histology in the target lesion.

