Seven milliliters of fasting blood will be collected at post-intervention for research biomarkers (1 x 7 ml SST tube for serum markers). SST tubes will be held at room temperature for 30 min followed by centrifugation. Serum will be aliquoted evenly into 10 x 1 ml cryovials. Cryovials will be labeled with the study ID, participant ID, and visit type (post). Samples will be stored at -80°C prior to analysis.

Saliva will be collected into a 50 ml conical tube for cytokine markers. Saliva will be aliquoted evenly into 10 x 1 ml cryovials. Cryovials will be labeled with the study ID, participant ID, and visit type (post). Samples will be stored at -80°C prior to analysis.

Twelve to fifteen formalin-fixed paraffin-embedded unstained tissue sections (4 µm) from biopsy collected at baseline and post-intervention will be requested from each institution's pathology department for measurement of tissue biomarkers.

Centralized pathology review

Centralized pathology review will occur for eligibility assessment and after study completion. The H&E stained section of the target lesion biopsy will be scanned by study personnel at each site using Aperio or equivalent scanner. [name] at UCSD will perform an independent centralized pathology review of the scanned slides.

In case of disagreement between the local site and central path review conducted by [name], the following actions will take place:

1. For minor discrepancy (one level change) in diagnoses, [name] evaluation will be considered final, for consistency.
2. For major discrepancy (two levels or more difference), the case will be referred to [name] at the NCI for independent review. The consensus evaluation of two pathologists in agreement will be used as the final diagnosis.
3. For disagreement among all three pathologists (local site, [name], and [name]), [name] and [name] will discuss the case and come to a consensus.

A designated UCSD site coordinator will be trained to compare the review from the local pathologist with the central pathology review and ensure timely notification to the site that the participant is eligible.

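### Histologic response is analysed only as the proportion improved, with worsened grades left out and no no-effect rate stated, so the planned output cannot tell a net shift from scatter

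*Combined protocol and SAP*

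**What the plan says.** Section 8.2.1 places each participant in one of four histologic categories. A complete response is a return to normal epithelium. The next category is "Partial Response (PR): Improvement of the degree of dysplasia or hyperplasia in the target lesion", with no minimum number of levels. Worsening is "Progressive Disease (PD): Increase in the severity of grade of histology in the target lesion". Everything else is no change.

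Section 13.5 then states that "the histologic response rate will be calculated and a one-sided 95% confidence interval based on the exact method will be derived". The sentence opens by likening this to the primary endpoint, but it names no reference rate for histology. The signed rank test in the same section is assigned to changes in tissue, serum and saliva markers; histologic grade is not named. No analysis in section 13 uses the histologic PD category.

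The reference rate in section 13.1, "30% is considered as poor treatment and a response rate of 60% is considered as a good treatment", is tied to clinical response in section 13.4.

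On sampling, section 7.6.3.2 takes the baseline punch from the centre or the clinically most suspicious area. Of the post-treatment sample it says: "The biopsy will be obtained from the most suspicious part of the lesion adjacent to the baseline biopsy". On reading, section 10.2 has a standing rule that begins "For minor discrepancy (one level change) in diagnoses" and lets the central evaluation stand in that case.

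**The concern.** The objective in section 1.2.1 is histologic response to metformin. With one arm, there is no control group to show how often a grade falls by a level between two biopsies when nothing has changed. Two features of the plan make such shifts possible. The paired grades come from different tissue, and one level is enough to count as a response.

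If scatter moves some participants down a grade, it should move others up. The participants who worsen are therefore the only information inside the trial on how large the scatter is. The planned statistic counts the first group and ignores the second. A rate of 40% could then be reported as histologic response to metformin when as many lesions had worsened as had improved.

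**Working it through.** **Inputs**
- Evaluable participants: n = 20. Section 13.3: "With a projected attrition rate of 20%, we anticipate to have at least 20 participants completing the agent intervention" (26 start; 26 × 0.80 = 20.8).
- Clinical reference rates: 30% and 60% (section 13.1); exact one-sided test at 5% (section 13.4).
- Chance that a grade improves or worsens without a drug effect: not given in the documents. All values below are assumptions, shown as a range.

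**Step 1. The plan's own figure.** With n = 20 and a null rate of 0.30, the smallest count with P(X ≥ r) ≤ 0.05 is r = 10, where P(X ≥ 10 | 0.30) = 0.048. Power is P(X ≥ 10 | 0.60) = 0.872. The stated 87% for the primary endpoint reproduces. Section 13.5 states no corresponding figure for histology.

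**Step 2. What the planned histologic output depends on.** The exact one-sided 95% lower bound for x improved of 20 is the 5th percentile of Beta(x, 21 − x). It is a function of x alone. The exact one-sided sign test uses both counts: p = P(B ≥ improved), with B ~ Binomial(improved + worsened, 0.5).

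| Improved | Worsened | Planned rate | Lower bound | Sign test p |
|---|---|---|---|---|
| 8 | 0 | 40% | 21.7% | 0.004 |
| 8 | 8 | 40% | 21.7% | 0.60 |
| 5 | 5 | 25% | 10.4% | 0.62 |
| 10 | 10 | 50% | 30.2% | 0.59 |

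This step needs no assumed noise rate. The last row shows that comparing the bound with 30% does not repair the problem: 10 of 20 clears 30% even if all the others worsened.

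**Step 3. What a bound above zero tells.** The bound exceeds zero as soon as one participant improves (1 of 20 gives 0.26%). If each participant has chance q of improving without a drug effect, the probability is 1 − (1 − q)^20:
- q = 5%: 64%
- q = 10%: 88%
- q = 20%: 99%

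It reaches 95% only when q is at least 1 − 0.05^(1/20) = 13.9%.

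**Step 4. How the sign test behaves at n = 20, one-sided 5%** (exact, summed over the number of changed grades).
- Symmetric noise, each way: 10% gives rejection in 0.9% of trials, 20% gives 2.0%, 25% gives 2.3%.
- No drug effect but drift towards improvement, improved/worsened: 20%/10% gives 9%, 25%/10% gives 17%, 30%/10% gives 26%.
- Power, improved/worsened: 40%/10% gives 49%, 50%/10% gives 70%, 60%/10% gives 85%.

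**The case against.** The strongest reply is that section 13.5 plans an estimate, not a claim. It sets no success rule, and none at zero. A reader might infer from Step 3 that noise alone would almost always produce a positive histologic finding. The documents do not support that. The probability in Step 3 is only the chance of at least one improver, it rests on a noise rate that the plan does not give, and it is 64% at 5%. It shows that a bound above zero carries no information, and no more. This part of the reply stands.

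Second, the reference to the primary endpoint may be meant to carry the 30% over. On that reading at least 10 of 20 must improve, and chance improvement alone reaches that in 0.26% of trials at 20% and 1.4% at 25%. But the text does not say that 30% applies to histology, and the last row of the table shows that worsened grades would still be ignored.

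Third, the one-level rule in section 10.2 concerns local against central readers and settles such cases with a single central evaluation. That reduces reader noise and says nothing about how often grades shift between visits. This stands, so the case rests mainly on the adjacent-site sampling in section 7.6.3.2.

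Fourth, section 13.4 says that interest lies in improvement, and PD will be recorded in any case. That justifies one-sided inference. It does not make the number worsened uninformative about scatter.

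Fifth, the sign test has its own weakness. The lesion with the worst histology becomes the target (sections 3 and 7.2) and baseline sampling favours the most suspicious area, so regression to the mean could favour improvement. The drift figures in Step 4 show the size. This stands and limits the test to a supportive role.

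**Conclusion.** The point holds in a bounded form. As planned, the histologic result is the same whether or not improvement is matched by worsening, so the rate and its bound cannot by themselves support an effect of metformin. The 8-of-20 contrast (p=0.004 against p=0.60 for the same 40% and 21.7%) follows from the plan's own definitions at n = 20 and needs no assumed noise rate.

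The chance of a bound above zero (88% to 99% at an assumed 10% to 20% chance improvement) and the sign test's error rates do rest on assumed rates. The low rejection of about 1% to 2% also needs noise to be symmetric.

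The consequence is moderate: this is a secondary endpoint of a single-arm phase IIa trial, and section 2.2 already defers any signal to a phase III study. It is nevertheless the first-ranked secondary endpoint, and the data needed for a better analysis are already collected.

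**What to change.** In section 13.5, keep the histologic response rate and its exact interval, and add text to this effect:

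*The numbers with histologic CR, PR, NC and PD will be reported together. As a supportive analysis, participants whose final central grade improved will be compared with those whose grade worsened by an exact one-sided sign test at 5%. The response rate alone will not be taken as evidence of a metformin effect. The test controls error only if chance shifts are symmetric, does not remove regression to the mean from selecting the worst lesion or the most suspicious area, and is not adjusted for multiplicity.*

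Name this one test, so that the choice is not left open between sign and signed rank. Say also whether the 30% reference is meant to apply to histology.

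The cost is a short change to the analysis text and one extra secondary test on grades already collected. The downside is a stricter reading of the histologic rate, with modest power if the true shift is small (49% at 40% improved and 10% worsened).
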